An effective PA intervention, implemented early in the chemotherapy treatment process, is needed to prevent the cycle of fatigue and inactivity in AYAs that is associated with negative outcomes.⁴ A multi-strategy intervention that includes components of education, negotiated goal-setting, and individualized feedback, can meet this need to enable AYAs to incorporate realistic goals to stay physically active on their own. During treatment, AYAs need to adjust PA goals based on their chemotherapy administration schedules and the predictable patterns of chemotherapy-related fatigue in order to prevent weeks of decreasing activity. Most studies report that PA is safe and well-tolerated by patients receiving chemotherapy, including patients with leukemia and lymphoma, which are common cancers in AYAs.¹⁰⁻¹² Patients receiving chemotherapy can safely begin a program of low-to moderate-intensity PA on their own.¹³⁻¹⁵ Furthermore, home-based approaches may result in better maintenance of PA for AYAs with cancer who are in active treatment and who may be unwilling or unable to travel to supervised programs at alternate locations.^{6, 16, 17}

Self-management is the dynamic process by which individuals integrate strategies to manage their disease, including management of treatment-related symptoms, such as fatigue. For individuals with a chronic disease, such as cancer, this self-management process will last a lifetime, requiring the adoption of healthy lifestyle habits. The Individual and Family Self-Management Theory (IFSMT) outlines factors related to the individual's knowledge and beliefs, self-efficacy and self-regulation, which impact the self-management process to improve outcomes.¹⁸ Self-efficacy is a predictive factor for participating in PA, and promoting AYAs' self-efficacy for PA needs to be explored as a strategy to improve self-management of fatigue.¹⁹

The purpose of this research is to study a 12-week PA intervention to improve self-management of fatigue in AYAs receiving chemotherapy. The intervention will include components of education, negotiated collaboration to set individual PA goals during chemotherapy cycles, and tools for self-monitoring PA. The aims of this study are:

1. To determine the impact of the PA intervention on the self-management process variables of self-efficacy and self-regulation and their relationships to PA and fatigue severity.

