2 BACKGROUND

Fatigue in Adolescents and Young Adults (AYAs) with Cancer

Fatigue is one of the most prevalent and severe symptoms in adolescents and young adults (AYAs) with cancer.² Defined as “a distressing, persistent, subjective sense of physical, emotional, and/or cognitive tiredness or exhaustion related to cancer or cancer treatment that is not proportional to recent activity”²⁰ (p1), cancer-related fatigue causes significant distress for AYAs and interferes with physical activities, social function, and mood.^{2, 21} AYAs commonly report that fatigue occurs with other troubling symptoms, such as poor sleep, nausea, and pain, and within these symptom clusters, fatigue is frequently named as the priority symptom.²² AYAs with cancer have shown greater symptom severity, including fatigue, than children and older patients.^{23, 24} The higher level of fatigue in AYAs may be due to their accelerated physical and cognitive growth, hormone-related changes, as well as their involvement in multiple activities of this developmental period (school, work, relationships, and parenting).³

Cancer-related fatigue is worst during the treatment period.^{2, 25} During cycles of chemotherapy, fatigue levels may follow a predictable and fluctuating pattern of increasing in the days after each cycle but improving before the next cycle.^{2, 26} Studies also show that fatigue may be a persistent long-term problem, even for AYAs who have completed treatment.^{2, 27, 28}

Physical Activity as an Evidence-based Intervention to Manage Fatigue in AYAs

Major oncology professional organizations recommend physical activity as an evidence-based intervention to manage fatigue, although most of this evidence comes from studies with adults who have the most common cancers, such as breast and prostate cancer.²⁹ Diverse PA programs for people with cancer have included aerobic and muscle-strengthening activities, such as walking, cycling, and yoga, and most programs last between 5 and 12 weeks.³⁰⁻³³

No trials have examined a PA intervention with YAs currently receiving treatment, and minimal PA studies have been conducted with patients who have the common diagnoses of this age group, such as lymphoma, leukemia, sarcoma, and germ cell tumors. A few PA interventions have targeted young adults with cancer who have completed cancer treatment, confirming that these patients are interested and able to participate in PA programs, especially when recommended by PA experts.³⁴⁻³⁶

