4. PATIENT SELECTION

Inclusion Criteria

Patients eligible for the study will be:

- 1) between the ages of 18 and 39 years of age;¹
- 2) have a diagnosis of cancer;
- 3) are within the first two months of a chemotherapy regimen that will last at least another 3 months;
- 4) are ambulatory without assistance;
- 5) have written consent from their physician to participate;
- 6) have the ability to understand English;
- 7) have access to a computer and the Internet.

The goal of this study is to deliver the intervention as early in the treatment period as possible, but we recognize that recruiting and completing baseline measures before chemotherapy begins may be a burden to patients and a barrier to recruitment. The lower age limit for AYAs will be set at 18 years rather than 15 years in order to use one set of instruments which have been validated only for adults over age 18 years. AYAs with any diagnosis of cancer will be included in this exploratory pilot study.

Exclusion Criteria

Patients will be excluded from enrolling in the study if they have symptoms of uncontrolled cardiopulmonary disease, uncontrolled neurological disease, delayed wound healing from surgery, a high risk of bone fracture, or pre-existing peripheral neuropathy. Physicians will be asked to give written approval to indicate that patients do not have any of these contraindications to physical activity.

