5. STUDY PROCEDURES

Recruitment Process

A member of the study team will screen clinic schedules at FH/MCW Cancer Center and clinic schedules in the Pediatric Hematology/Oncology Clinic to identify every AYA who meets the inclusion criteria. Clinic staff will ask eligible patients if they are willing to speak

with a member of the study team about the study. Eligible participants will be given time - over days, if necessary and possible - to consider study participation after hearing the details of the study. A member of the study team will complete the informed consent process with AYAs using an open exchange, reading through the informed consent document together, and allowing for assessment of comprehension and discussion of questions and concerns. A member of the study team will obtain written consent from the patient's primary provider to indicate the patients do not have any contraindications to physical activity.

A signed informed consent form copy will be given to the subject and a copy will be filed in the medical record. The original will be kept on file with the study records.

All patients who are consented will be registered in OnCore[®], the MCW Cancer Center Clinical Trial Management System. The system is password protected and meets HIPAA requirements.

Study Procedures

1. Visit 1 Enrollment

Following informed consent, a study team member will administer baseline surveys to all participants. Participants will receive instructions about wearing an accelerometer (Actigraph) for 1 week and how to return the accelerometer (Actigraph).

Participants will be asked for their preferred method of contact (email or phone call) to be reminded to return the accelerometer after one week of wear. A study team member will contact participants after the one-week period and remind them to return the accelerometer promptly in the mailing envelope that was provided.

Participants will be randomized to the intervention group or the usual care group.

2. Visit 2 (next regularly scheduled visit for chemotherapy)

Intervention group participants will meet with the facilitator, who will provide initial education about the benefits of physical activity and strategies to overcome barriers to physical activity, help the participants to set physical activity goals based on ability and preferences, and educate the participant on using a physical activity tracker (Fitbit Flex).

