Usual care group participants will meet with the facilitator who will provide initial information to participants about the study and a published flyer about general guidelines for physical activity during treatment.

3. Visits 3, 4, 5, 6 (next regularly scheduled visits for chemotherapy – at intervals of approximately 3 weeks but may range from every 2-4 weeks based on chemotherapy schedule)

Intervention group participants will meet with the facilitator who will deliver a 30 minute intervention: 1) review physical activity summary over the past weeks, 2) identify barriers and discuss strategies to overcome barriers to physical activity, and 3) revise physical activity goals as needed. The facilitator will record physical activity data from the tracking device (Fitbit Flex), discussion notes about the barriers and strategies, and physical activity

goals. Any experiences or complications that might affect physical activity will be recorded, such as hospitalizations.

Usual care group participants will meet with the facilitator to maintain engagement in the study. The facilitator will record any experiences or complications that might be pertinent to the study, such as hospitalizations and enrollment in any activities related to physical activity.

At study visit 6, all participants will complete post-study surveys and will receive instructions about wearing an accelerometer (Actigraph) for 1 week and how to return the accelerometer (Actigraph).

A study team member will contact participants after the one-week period and remind them to return the accelerometer promptly in the mailing envelope that was provided.

Following completion of the study, a member of the study team will ensure completion and return of accelerometer (Actigraph) use by all participants. All participants will receive \$25 compensation. Intervention participants will complete an additional post-study survey to evaluate components of the intervention and be invited to keep the physical activity tracker (Fitbit Flex).

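### Fatigue is scored at a chemotherapy visit post-study but on no set cycle day at baseline, so each group's baseline-to-post change can reflect cycle phase; the comparison between arms is not biased

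*Combined protocol and SAP*

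**What the plan says.** Fatigue (PROMIS-29 and the PROMIS Fatigue Short Form) is scored twice, at Visits 1 and 6 (Study Calendar; Section 3, instrument table).

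- **Post-study.** Section 5: "At study visit 6, all participants will complete post-study surveys and will receive instructions about wearing an accelerometer (Actigraph) for 1 week". Visit 6 belongs to the group headed "Visits 3, 4, 5, 6 (next regularly scheduled visits for chemotherapy", held "at intervals of approximately 3 weeks but may range from every 2-4 weeks based on chemotherapy schedule".
- **Baseline.** Section 5: "Following informed consent, a study team member will administer baseline surveys to all participants". Before that, "Eligible participants will be given time - over days, if necessary and possible - to consider study participation". Section 4 admits patients who "are within the first two months of a chemotherapy regimen that will last at least another 3 months". No cycle day is set for Visit 1.
- **Fatigue within a cycle.** Section 2: "fatigue levels may follow a predictable and fluctuating pattern of increasing in the days after each cycle but improving before the next cycle". Section 1 adds that "AYAs need to adjust PA goals based on their chemotherapy administration schedules and the predictable patterns of chemotherapy-related fatigue", the stated purpose being to avoid weeks of falling activity.
- **Analysis.** Section 6, Aim 2, examines baseline-to-post differences within each group and then compares the groups with t-tests. Aim 1 places steps per day between the process variables and fatigue as the second mediator.

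Neither the data collection plan nor the covariate plan mentions days since infusion or cycle phase. Section 6 says only that variables with notable variation will be explored as covariates. The recall period of the fatigue instruments is not stated.

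**The concern.** The protocol describes a fatigue pattern tied to the chemotherapy cycle and asks patients to plan activity around it, but leaves it out of the outcome schedule. The post-study score is pinned to the end of a cycle. The baseline score may fall shortly after an infusion, in mid-cycle or just before the next infusion.

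Three things are at stake:

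1. **Within-group changes.** If baseline is spread over the cycle and the post-study score is always late in it, both arms can appear to improve with no real change. The plan reports these changes for each group, and in a pilot they are likely to be read as evidence.
2. **Precision and coverage.** Phase differences between patients add noise to change scores. With a short recall period, the days just after infusion are not covered by the post-study score.
3. **Mediator and outcome.** The post-study accelerometer week starts at Visit 6. Steps are therefore recorded after the fatigue score they are meant to explain, and in the days after an infusion rather than before one.

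**Working it through.** **Inputs from the documents.** 34 per group analysed and a 0.10 significance level (Section 6, Sample Size); visit intervals of 2 to 4 weeks (Section 5). The plan's 68 reproduces closely: a four-predictor regression F test with f² = 0.15 (assumed for a medium effect) at alpha 0.10 has 79.6% power at N = 68. The timing point does not depend on that figure.

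**Assumptions, because the documents give no values.** Fatigue falls in a straight line over the cycle from peak to trough by S points, with S = 3, 5 or 10. Visit 1 is uniform over the cycle and Visit 6 is at the trough. Change-score SD without phase noise is 10. The true difference between arms is 5 points, tested two-sided at 0.10.

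**Step 1: apparent improvement in each arm.** Under a uniform phase, the mean excess of baseline over the trough is S/2: 3/2 = 1.5, 5/2 = 2.5, 10/2 = 5.0 points. If every Visit 1 is also a chemotherapy visit, it is 0.

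**Step 2: added noise.** The phase SD is S/√12, and the change-score SD becomes √(10² + S²/12). Power is for a two-sample t-test with 34 per arm.

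| S | Phase SD | Change-score SD | Power |
|---|---|---|---|
| 0 | 0 | 10.00 | 65.4% |
| 3 | 0.87 | 10.04 | 65.1% |
| 5 | 1.44 | 10.10 | 64.6% |
| 10 | 2.89 | 10.41 | 62.4% |

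The loss is 0.3, 0.8 or 3.0 percentage points.

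**Step 3: sensitivity to the baseline-post correlation.** Take a true difference of 0.5 SD, where SD is that of a single score, and swings of 0, 1 and 2 SD. Power is 53%, 51% and 46% at correlation 0.3; 65%, 62% and 55% at 0.5; and 84%, 80% and 68% at 0.7. Only a swing as large as 2 SD costs much, about 7 to 16 points.

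**Step 4: the difference between arms.** The shift in Step 1 has the same expectation in both arms. The expected difference in mean change is therefore 5 + S/2 − S/2 = 5 for every S.

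**Step 5: what Visit 6 can cover.** With an assumed 7-day recall, a score at the end of a cycle reaches back to day 14 − 7 = 7, 21 − 7 = 14 or 28 − 7 = 21 of a 2-, 3- or 4-week cycle. The first week after infusion is not covered. A recall as long as the cycle would cover all of it.

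**Step 6: order of steps and fatigue.** At Visit 6 the survey is completed and the accelerometer week then begins. The survey looks back over the end of one cycle, and the steps come from the week after that visit.

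**The case against.** The strongest reply is that the trial judges efficacy by comparing randomized groups, and that comparison is sound. Section 5 lists baseline surveys before randomization, and Visit 6 has the same timing in both arms, so a common shift cancels (Step 4). This stands. A reader might infer from the mismatch that the arm comparison is biased; the documents do not support that.

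A reader might also infer that the intervention works mainly by blunting the peak after infusion, so that Visit 6 could not show its effect. The documents do not support this either. Sections 1 and 2 give the rationale as preventing a cumulative cycle of fatigue and inactivity, which could show in a pre-infusion score. Missing the peak also needs a short recall period, which is not stated; the instrument table lists frequency and duration of fatigue, which describe a period rather than a moment.

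Three further replies have weight:

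- Patients are found from clinic schedules, and Visit 2 is described as the next chemotherapy visit, so many baselines may also fall on chemotherapy days. Phase mixing is possible, not shown.
- Section 2 says only that fatigue may follow the pattern. Nor is Visit 6 certain to be a chemotherapy visit: with 4-week intervals, Visits 2 to 6 span 4 × 4 = 16 weeks, which can exceed the further three months of treatment required at entry.
- The peak day is not given and regimens vary, so any single post-infusion day is debatable. A pre-infusion visit is at least a consistent phase.

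These points limit the size of the problem. They do not supply an alignment rule, a record of cycle day, or an explanation of why steps follow the fatigue score.

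**Conclusion.** The point holds as a cheap improvement, not as a threat to the randomized comparison. The two fatigue scores are not tied to the same cycle phase and phase is not recorded, so the planned within-group changes cannot be separated from cycle timing. Under the assumed swings of 3 to 10 points and a uniform baseline phase, the artefact is 1.5 to 5.0 points of apparent improvement in each arm; it is zero if Visit 1 is always a chemotherapy visit. The cost to the arm comparison is small, about 0.3 to 3 percentage points of power for a 5-point difference with change-score SD 10. Loss of the first post-infusion week is conditional on a recall period of about a week or less. The order of post-study steps and fatigue follows directly from the schedule and weakens the reading of steps as a mediator.

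**What to change.** 1. Require the baseline and post-study fatigue surveys at the same cycle phase, with the baseline survey still completed before randomization. The simplest form is a pre-infusion survey at a chemotherapy visit both times.
2. Record days since last infusion at each survey, and name the baseline value as a covariate in the fatigue analysis. State the recall period of each fatigue instrument, and what happens if the regimen ends before Visit 6.
3. Preferably also send the REDCap fatigue survey at the existing one-week accelerometer-return contact, at baseline and post-study, with both accelerometer weeks starting on an infusion day. Fatigue and steps then cover the same days. Keep the Visit 6 clinic score as a pre-infusion measure. If the one-week baseline survey is used, randomization must follow it. Section 5 gives the initial education at Visit 2 but the Study Calendar shows it at Visit 1, so those passages must be reconciled first.
4. Describe within-group changes as descriptive, and report them with cycle day.

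The cost is protocol wording, one extra data field and a scheduled survey invitation. Surveys are already electronic, Internet access is an entry criterion, and the one-week contact exists at both ends. The downsides are that some remote surveys may be late or missed, and that baseline may wait a few days, at most until the next infusion.

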6. STATISTICAL ANALYSIS

Sample Size

In an a priori power analysis using a mediation model that includes 4 predictors (intervention variable, self-efficacy, self-regulation, and PA), a total sample of 68 participants (34 in each group) would be needed to detect a medium-sized effect at a 0.10 significance level with 80% power. The power analysis was completed by using an online sample size calculator (<http://www.danielsoper.com/statcalc/calculator.aspx?id=1>) based on the above information. Physicians at FH/MCW and CHW saw approximately 300 AYAs with a new cancer diagnosis in 2012, and about half of those AYAs received chemotherapy. Assuming a 50% enrollment rate and 10% attrition, 75 AYAs will be recruited from these sites for a final sample of 68.

Data Management and Analysis

Questionnaire data will be collected electronically using REDcap surveys, and accelerometer (Actigraph) data will be analyzed using respective software. For the intervention group, weekly PA data will be transcribed from the PA tracker (Fitbit Flex) dashboard to REDcap files at each visit. All REDcap data will be exported to SPSS for analysis. Descriptive statistics will be used to describe and summarize the context variables related to the sample. Variables with significant patterns of variation will be explored as potential covariates. Missing values will be identified and reviewed for patterns of missingness, and the percentage of missing data will be calculated. If missing data are less than 5%, pairwise deletion will be used in data analysis, meaning all available cases will be used. If missing data are greater than or equal to 5%, Little's Chi-square test will be used to check if data are missing at random. If missing at random is assumed, multiple imputation method will be used. Field notes from sessions with the facilitator related to barriers and self-management strategies as well as notes from post-study debriefing interviews will be recorded and organized by participant visit.

After all study queries and analyses are completed, the data/PHI will not be destroyed but will be archived in a secure long-term storage site in order to keep an accurate record of screened and enrolled subjects for the sponsor and potential audit purposes only specific for this study. Data/PHI would not be destroyed until permission is granted by the sponsor to destroy the records.

Statistical Analyses

Specific Aim 1: To determine the impact of the PA intervention on the self-management process variables of self-efficacy and self-regulation, data analysis will examine differences in baseline and post-study measures of self-efficacy and self-regulation for each group. Group differences will be compared using t-tests to determine the effect of the intervention on these process variables. A mediation model will be used to describe the relationships of self-management process variables (self-efficacy and self-regulation) to PA (steps/day by accelerometer) and fatigue severity where self-efficacy and self-regulation are the main mediators of the intervention, PA is the second mediator, and fatigue severity is the dependent variable. The direct and indirect effect of treatment on PA and fatigue severity will be determined by the following steps:^{45, 46}

- Step 1. The regression of the fatigue severity on the intervention variable, ignoring the mediators, is significant.
- Step 2: The regression of the main mediators on the intervention variable is significant.
- Step 3: The regression of the second mediator (PA) on the main mediators (self-efficacy and self-regulation), controlling for the intervention, is significant.
- Step 4: The regression of the fatigue severity on the second mediator (PA), controlling for the main mediators (self-efficacy and self-regulation) and the intervention, is significant.
- Step 5: The regression of the fatigue severity on the intervention, controlling for the mediators, is non-significant and nearly-zero. In this case, the effect of intervention on fatigue severity is indirect through the mediators. If regression of the fatigue severity on the intervention, controlling for the mediators, is still significant, then the effect of treatment on fatigue severity is direct.

From the regression models, unstandardized regression coefficients and their standard errors will be calculated for the associations between the intervention variable and the mediators as well as between the fatigue severity and the mediators. The Sobel test will be used to test if the mediation effect is statistically significant.⁴⁵⁻⁴⁹ Data from field notes from the intervention group participants will be analyzed using qualitative, inductive content analysis procedures to identify themes related to self-efficacy and self-regulation skills.

Specific Aim 2: To determine the preliminary efficacy of the PA intervention on outcome variables of PA (steps/day by accelerometer) and fatigue severity, data analysis will examine differences in baseline and post-study measures of PA (steps/day by accelerometer) and fatigue severity (PROMIS-29 and PROMIS Fatigue scores) for each group. Group differences will then be compared using t-tests to detect the effect of the PA intervention on these outcomes. Direct and indirect effect of the intervention on fatigue severity will be studied using the mediation model discussed in Aim 1. Quantitative data about the fidelity of the intervention will be used to estimate the dose of the delivered intervention for each participant and to explore whether there was a dosage effect on the outcomes.

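### Little's test, whose null is MCAR, decides whether data count as MAR; no analysis follows if MAR is not assumed, and the 5% trigger has no denominator

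*Combined protocol and SAP*

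**What the plan says.** Section 6 (Statistical Analysis), under Data Management and Analysis, sets the rule. Missing values are "reviewed for patterns of missingness, and the percentage of missing data will be calculated". Then: "If missing data are less than 5%, pairwise deletion will be used in data analysis, meaning all available cases will be used". At 5% or above, Little's "Chi-square test will be used to check if data are missing at random". The only action attached to that check is: "If missing at random is assumed, multiple imputation method will be used".

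The section gives no level for Little's test, does not say what the percentage is taken over, and names no analysis for the case where MAR is not assumed. The paragraphs on Specific Aims 1 and 2 do not mention missing data. For Aim 1, "data analysis will examine differences in baseline and post-study measures of self-efficacy and self-regulation for each group", followed by between-group t-tests, a sequence of regressions and a Sobel test. Aim 2 treats steps per day and fatigue in the same way.

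The expected loss is under Sample Size: "Assuming a 50% enrollment rate and 10% attrition, 75 AYAs will be recruited from these sites for a final sample of 68".

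**The concern.** Three properties have to be kept apart. Under MCAR, missingness is unrelated to any data. Under MAR, it may depend on observed values, such as baseline fatigue, but not on the missing value once those are known. Under MNAR (missing not at random), it still depends on the missing value. Multiple imputation is valid under MAR, given a suitable imputation model. Little's test compares observed means across missingness patterns, and its null is MCAR. It cannot separate MAR from MNAR, because that distinction depends on values nobody has seen.

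The rule therefore asks the test a question that it cannot answer. If dropouts had worse baseline scores and the test rejects, MAR may well hold and imputation is useful, yet the natural reading is that imputation is no longer available, and nothing replaces it. If the test does not reject, MAR has not been shown.

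The 5% trigger is a separate gap. Per variable, per participant and over all cells are all admissible counts. Two analysts could follow the text and run different analyses on the same data.

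**Working it through.** **1. The plan's own figure.** 75 × (1 − 0.10) = 67.5, rounded to 68, so 75 − 68 = 7 losses. Ten percent of 75 is 7.5, so 7 and 8 are the nearest whole counts.

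**2. The 5% under different counts.** The instrument table in Section 3 lists five instruments given before and after (self-efficacy, self-regulation, accelerometer, PROMIS-29, PROMIS Fatigue) and three baseline-only forms. Assume that each lost participant has all baseline data and no post-study data, and count each instrument once per time point.

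| Count | 7 lost | 8 lost |
|---|---|---|
| Per post-study variable (or participants with any gap) | 7/75 = 9.3% | 8/75 = 10.7% |
| Five instruments, both times | 35/750 = 4.7% | 40/750 = 5.3% |
| Same plus three baseline-only forms | 35/975 = 3.6% | 40/975 = 4.1% |

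If losses are independent at 10% (binomial, n = 75), the per-variable count reaches 5% from 4 losses (4/75 = 5.3%), with P(X ≥ 4) = 0.950. The five-instrument pooled count reaches it from 8 losses, with P(X ≥ 8) = 0.479.

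**3. What the test responds to.** Simulation with one baseline and one post-study score, correlation 0.6, 7 of 75 post-study values missing, fairly strong selection (weight multiplied by exp(1.5) per SD), level 0.05, 4,000 runs; all settings except 7 of 75 are assumed. Rejection rates:

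- MCAR: 5.6%
- MAR through the observed baseline: 94.2%
- MNAR through the unobserved part of the outcome: 4.7%
- MNAR through the outcome itself: 50.5%

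The test rejects where imputation is valid and stays at its nominal rate in one case where it is not.

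For milder departures, take a baseline difference of d SD between m dropouts and the rest, with noncentrality λ = d² × m(75 − m)/75. For m = 7, 7 × 68/75 = 6.35; for m = 8, 8 × 67/75 = 7.15. So λ is 1.59 to 1.79 at d = 0.5 and 6.35 to 7.15 at d = 1. Over 4 to 11 degrees of freedom and levels 0.05 to 0.10 (assumed), rejection is 10–25% at d = 0.5 and 33–67% at d = 1.

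**4. Effect on the arm difference.** Simulated MAR dropout: 38 versus 37, no true effect, four complete baseline scores, 10% missing post-study, logit slope 1 per SD of baseline, correlation 0.6, level 0.05, 6,000 trials per setting. The last column applies the plan's rule, with complete cases after rejection (an assumption, since the plan names nothing) and regression-based imputation otherwise.

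| Dropout depends on baseline | Test rejects | Bias in SD if never imputed, post / change | Bias in SD under the rule, post / change |
|---|---|---|---|
| Alike in both arms | 42% | 0.00 / 0.00 | 0.000 / −0.002 |
| Intervention arm only | 13% | −0.056 / +0.035 | −0.010 / +0.005 |
| Opposite directions | 7% | −0.114 / +0.068 | −0.007 / +0.004 |

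The sampling SD of the arm difference is 0.22 to 0.24. A separate run of the opposite-direction case gave −0.008 for post-study scores. Among only those trials in which the test rejects, the opposite-direction bias is still about 0.09 SD. Regression on arm and the baseline scores leaves at most 0.005 SD in every MAR setting.

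**5. Missing not at random.** With dropout driven by the unobserved part of the post-study score, in opposite directions by arm, the test rejects 4.8% of the time. Bias is −0.147 (post) and −0.145 (change), and adjusting for baseline leaves −0.145. Imputation under MAR would not remove it, with or without the test.

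**The case against.** The strongest reply is that the rule does little harm on average. Non-rejection leads to imputation, so the test matters only when it rejects. In the simulated settings it rejects often where dropout acts alike in both arms and no bias arises, and seldom where complete cases would be biased. That stands: a reader who took −0.11 and +0.07 SD as the cost of the rule would overstate its average effect about tenfold or more.

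The wording also leaves room. Imputation depends on MAR being assumed, after a review of missingness patterns. An analyst could reject MCAR, still assume MAR and impute, and the text does not forbid it. That stands too, but it leaves the choice of method open until the data are seen. If MAR was loose wording for MCAR, rejection would still point away from imputation where it is useful.

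On the denominator, per variable is the usual reading, and the five-instrument pooled count falls below 5% only narrowly: one more loss takes both counts over. The ambiguity is real, but the example sits close to the threshold.

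A reader might also expect step counts to suffer further loss because monitors are returned by mail. The documents give no non-return rate. They do plan for return: staff will "remind them to return the accelerometer promptly in the mailing envelope that was provided", and are to see that return is completed. No figure for lost step data can be drawn from them.

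Finally, the protocol describes an exploratory pilot seeking preliminary efficacy. That lowers the stakes. It does not make an undefined branch usable.

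**Conclusion.** The point holds as a defect in the rule. A test of MCAR is asked to settle MAR, the branch where MAR is not assumed has no analysis, and the 5% has no denominator although the planned 7 losses fall on either side of it (9.3% or 4.7%). This follows from the text and the plan's own attrition figure and needs no simulation.

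Three stronger readings are not supported:

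- **That the rule materially biases the arm difference.** Its average effect is about 0.01 SD or less under simulated MAR dropout, against a sampling SD of 0.22 to 0.24. The larger complete-case biases arise only if imputation is not used, and the MNAR bias of about −0.15 SD is the same with or without the test.
- **That imputation is forbidden after rejection.** It is only left unprovided for.
- **That the denominator always changes the analysis.** At 8 losses the per-variable and five-instrument counts lead to the same branch.

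The simulated sizes rest on assumed dropout strength and direction, correlation, degrees of freedom and test level. The only level the plan states is 0.10, for the sample size. The mediation and Sobel results were not simulated. The plan should be amended, but this is not a flaw that invalidates the trial.

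**What to change.** In Data Management and Analysis:

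- Remove Little's test as the condition for imputation and state MAR as an assumption. Report the test, with its level, only as a description of departure from MCAR.
- Define the 5% as the percentage missing on any variable that enters the analysis, baseline or post-study, including accelerometer steps.
- When any such variable reaches 5%, use multiple imputation whatever the test shows, with arm and all baseline and post-study analysis variables in the imputation model.
- Use the same imputed sets for the t-tests and every mediation regression. Pool coefficients and standard errors by Rubin's rules before the step for which the plan says "The Sobel test will be used to test if the mediation effect is statistically significant".
- Optionally, add a sensitivity analysis that shifts imputed post-study fatigue and steps in one arm over a range fixed in advance.

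The cost is a few sentences and modest analysis time, with no new data, visits or participants. The limit is that imputation under MAR does not remove bias from data missing not at random; the optional shift analysis only shows how far the conclusions depend on that assumption.
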